5.4 Dosage Adjustments

5.4.1 Withholding of Study Drug

Subjects with symptomatic orthostatic hypotension and/or systolic BP <85 mmHg, which in the medical judgment of the Investigator would interfere with subject's ability to safely receive study drug, will have study drug withheld until the next scheduled monthly administration, but should still have all other study visit assessments completed. If study drug is withheld and subsequently rescheduled, central laboratory assessments required for that visit will need to be repeated if they were drawn >7 days prior to the rescheduled dosing date. A symptom-directed physical exam and vital signs need to be repeated prior to each dosing.

5.4.2 Management of Suspected Systemic Infusion-Related/Hypersensitivity Adverse Events

In the event of a suspected systemic infusion-related and/or hypersensitivity AE, the infusion should be immediately discontinued and appropriate supportive therapy should be administered per institutional practice, which may include, but is not limited to, epinephrine, IV fluids, corticosteroids, vasopressors, oxygen, bronchodilators, antihistamines, or acetaminophen/paracetamol. Subjects should be evaluated and carefully monitored until there is complete resolution of the AE (i.e., all hypersensitivity signs and symptoms have resolved). In addition to the institution's recommended assessments, blood samples should be obtained in the event of a suspected systemic infusion-related and/or hypersensitivity AE for assessment of the following: cytokine levels (IL-6, IL-8, TNF-alpha, and INF-gamma) complements C3, C4, and CH50; C-reactive protein (CRP), serum amyloid A/acute phase serum amyloid A (SAA/A-SAA); tryptase (serial levels: within 30 to 120 minutes of onset AND at 48 to 72 hours); serum NEOD001; and anti-NEOD001 antibody levels. If possible, samples should be collected while the acute symptoms persist.

For subjects with a Grade 2 infusion-related AE, if it is appropriate to restart the infusion, the infusion rate should be decreased by 50% (e.g., if the infusion was previously administered over 60 minutes, the new rate should be based on administering 250 mL over at least 90 minutes). If the subject is to receive additional infusions in subsequent weeks, the rate of these infusions should be discussed with and agreed upon prospectively by the Investigator and the Medical Monitor. In addition, for all subsequent infusions, maximal premedication must be administered according to institutional practice and should include an H1 blocker, an H2 blocker, an antipyretic such as acetaminophen/paracetamol and a steroid (e.g., 25-50 mg hydrocortisone IV).

If a subject experiences a Grade 3 infusion-related and/or hypersensitivity AE, the infusion should not be restarted. The decision to continue dosing this subject at their next scheduled administration should be discussed with the Medical Monitor. If the decision is made to proceed with subsequent dosing, **both** the dose and infusion rate will be reduced by 50% from the original dose (i.e., 12.5 mg/kg in 250 mL) and infusion rate (e.g., over at least 90 minutes [if the previous infusion time was 60 minutes]). In addition, maximal premedication must be administered according to institutional practice and should include an H1 blocker, an H2 blocker, an antipyretic such as acetaminophen/paracetamol and a steroid (e.g., 25-50 mg hydrocortisone IV). Subjects who have an infusion-related and/or hypersensitivity AE at the subsequent scheduled study drug administration must have study drug permanently discontinued and have an ETD Visit per Section 6.1.3.

Subjects who experience a Grade 4 infusion-related and/or hypersensitivity AE must have study drug permanently discontinued and have an ETD Visit per Section 6.1.3.

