5.3 Dosage, Preparation, and Administration

Study drug consists of NEOD001. The NEOD001 dose is 24 mg/kg; however, the maximum dose administered is not to exceed 2500 mg. Therefore, subjects with a weight of 104.2 kg or greater will receive the maximum dose of 2500 mg. The subject's weight during Screening may be used for calculation of the first dose. Subsequent doses may be calculated based on the current weight at that visit or using the Screening weight, based on the site's institutional guidelines. A change of $\pm 10\%$ from the weight being used for dosing should trigger recalculation of the dose based on the new weight unless thought to be exclusively due to fluid fluctuation (e.g., edema).

Each vial of 500 mg of NEOD001 will be reconstituted with 9.6 mL sterile WFI to a concentration of 50 mg/mL resulting in a buffered, isotonic, preservative-free solution with a total extractable volume of 10 mL. Study drug will be prepared in a 250 mL IV bag of 0.9% saline. The equivalent volume of reconstituted NEOD001 will be withdrawn prior to transferring the drug solution into the IV bag, such that the total IV bag volume will be 250 mL. Refer to the Pharmacy Manual for complete information on preparing and administering the study drug.

The Pharmacy Staff at each site will be responsible for preparing the study drug.

The study drug should only be administered in settings where emergency resuscitative equipment and personnel trained in the management of anaphylaxis are immediately available to treat systemic reactions under the direct supervision of a physician.

NEOD001 will be administered once every 28 days (a ± 5 -day window is allowed for visits starting after Month 1) over 60 (± 10) minutes unless a longer infusion duration was established for the individual subject in Study NEOD001-201. A minimum of 21 days between doses is required. The length of the infusion may be extended over a longer period of time if and when it is clinically indicated.

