9.3. Adverse Events

Verbatim terms on the OLE Adverse Event eCRFs will be mapped to PT and SOC using MedDRA version 19.0. AEs will be reported, and severity will be categorized using the Common Terminology Criteria for Adverse Events (CTCAE, Version 4.03).

All AE summaries will be restricted to treatment-emergent adverse events (TEAEs), which are defined as any AE that newly appears, increases in frequency, or worsens in severity following initiation of study drug and up to 30 days after date of last dose or last study visit, whichever is

later. If it cannot be determined whether the AE is treatment emergent due to a partial onset date, then it will be counted as such.

To assess the long-term treatment effects overall and relative to shorter term treatment, TEAE incidence will be summarized separately by the original parent study (NEOD001-201) and OLE study (NEOD001-OLE251) as shown in Table 6. TEAEs collected during original parent study will be summarized by actual treatment subjects received. TEAEs that start on or after the first dose of OLE study will be summarized by treatment group subjects received in parent study. Overall summary will also be presented for NEOD001-OLE251.

Table 6: Treatment Group Schema

NEOD001-201		NEOD001-OLE251		
NEOD001 (N=xx)	Placebo (N=xx)	NEOD001-201 NEOD001 (N=xx)	NEOD001-201 Placebo (N=xx)	Overall (N=xx)

Each AE summary will be presented according to Table 6 for All Treated Subjects. Summaries that are displayed by SOC and PT will be ordered by descending order of NEOD001-OLE251 overall incidence of SOC and PT within each SOC.

- An overall summary of AE incidences will be presented, including the number and percent of subjects with at least one of:
 - Any TEAE
 - TEAE by maximum CTCAE Grade
 - CTCAE Grade ≥ 3 TEAE
 - Serious TEAE
 - Fatal TEAEs (outcome="Fatal" or severity=CTCAE Grade 5)
 - Treatment-related TEAE
 - Treatment-related serious TEAE
 - Treatment-related TEAE of CTCAE \geq Grade 3
 - TEAE leading to infusion interruption
 - TEAE leading to dose reduction
 - TEAE leading to dose being held
 - TEAE leading to prolongation of infusion time (>2.5 hours)
 - Infusion associated TEAE as determined by the Investigator
 - TEAE leading to study drug withdrawal
- Subject incidence of TEAEs by MedDRA SOC and PT
- Subject incidence of serious TEAEs by MedDRA SOC and PT

The following listings will be presented by subject for OLE Safety Population:

- All AEs

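### Protocol 5.4.2 orders a 50% rate cut after a Grade 2 or 3 infusion reaction, but its 90-minute example gives only 33%, and 12.5 mg/kg is not half of 24 mg/kg

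*Protocol*

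**What the plan says.** Protocol 5.3 sets the regimen: "The NEOD001 dose is 24 mg/kg; however, the maximum dose administered is not to exceed 2500 mg". It is prepared in a 250 mL bag and infused over 60 (±10) minutes unless a longer time was established in the parent study. On the cap, the same section says that "subjects with a weight of 104.2 kg or greater will receive the maximum dose of 2500 mg".

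Protocol 5.4.2 covers what follows a reaction.

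- **Grade 2, if a restart is appropriate:** "the infusion rate should be decreased by 50% (e.g., if the infusion was previously administered over 60 minutes", and then "the new rate should be based on administering 250 mL over at least 90 minutes". The Medical Monitor enters at the next step: "If the subject is to receive additional infusions in subsequent weeks, the rate of these infusions should be discussed with" that person and agreed in advance.
- **Grade 3, if dosing continues at the next scheduled visit:** "the dose and infusion rate will be reduced by 50% from the original dose (i.e., 12.5 mg/kg in 250 mL) and infusion rate", with the time illustrated as "over at least 90 minutes [if the previous infusion time was 60 minutes".

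Neither document defines a rate cut as a lengthening of the infusion, and neither gives an original dose of 25 mg/kg.

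**The concern.** The rule and the figures attached to it disagree. Rate is volume over time, so halving the rate of a fixed volume doubles the time. Sixty minutes should become 120, not 90. Likewise, half of 24 mg/kg is 12 mg/kg.

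This is the instruction for re-exposing a subject who has just reacted to the drug. Staff at the chairside are likely to use the worked number, and any time from 90 to just under 120 minutes satisfies the example while breaking the rule. In the Grade 2 restart the dose is not automatically reduced, and Medical Monitor agreement is written only for later infusions. The rate is therefore the main protection the text specifies for that restart. The Grade 3 dose figure follows *i.e.* rather than *e.g.*, so it reads as the dose to give. The section does not restate the cap alongside it.

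**Working it through.** **Inputs.** Bag volume 250 mL and dose 24 mg/kg, maximum 2500 mg (Protocol 5.3). Stated cut 50%, previous time 60 minutes, new time at least 90 minutes, and Grade 3 dose 12.5 mg/kg (Protocol 5.4.2).

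**Where the plan's figures could come from.** 60 × 1.5 = 90 minutes, which is the time lengthened by 50% instead of the rate cut by 50%. 12.5 × 2 = 25 mg/kg, so 12.5 is half of 25, not of 24. These origins are inferences; the documents do not explain either figure.

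**Infusion rate** = volume / time.

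| Time (min) | Rate (mL/min) | Cut from 60 min |
|---|---|---|
| 60 | 250/60 = 4.17 | none |
| 90 | 250/90 = 2.78 | 1 − 60/90 = 33.3% |
| 120 | 250/120 = 2.08 | 1 − 60/120 = 50% |

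Rate at the 90-minute floor relative to the rule: 2.778/2.083 = 1.33.

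The ±10-minute allowance does not rescue the figure. From 50 minutes, 90 minutes is a cut of 1 − 50/90 = 44% (halving needs 100 minutes). From 70 minutes it is 1 − 70/90 = 22% (halving needs 140 minutes).

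**Grade 3 drug delivery** = dose / time.

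- Original: 24/60 = 0.400 mg/kg/min.
- As written, at the floor: 12.5/90 = 0.139 mg/kg/min, a fall of 65%.
- Dose and rate both halved: 12/120 = 0.100 mg/kg/min, a fall of 75%.

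**Grade 3 dose.** 24/2 = 12 mg/kg. The stated figure is 12.5/24 = 52.1% of the original, and 12.5/12 = 1.042, or 4.2% above half.

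For capped subjects, half of the maximum is 2500/2 = 1250 mg. If a site gave 12.5 mg/kg instead:

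| Weight (kg) | Dose at 12.5 mg/kg | Share of 2500 mg |
|---|---|---|
| 104.2 (cap threshold) | 1302.5 mg | 52.1% |
| 110 (assumed) | 1375 mg | 55% |
| 120 (assumed) | 1500 mg | 60% |
| 130 (assumed) | 1625 mg | 65% |

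The documents give no weight distribution, so the last three rows are illustrations only.

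**Effect on the SAP.** SAP 9.1 summarizes exposure by duration and number of infusions, not by milligrams. SAP 9.3 counts events leading to dose reduction whatever the size of the cut. Its category "TEAE leading to prolongation of infusion time (>2.5 hours") starts above 150 minutes, so 90 and 120 minutes both fall outside it.

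**The case against.** The strongest reply is that the operative rule is sound. The text orders a 50% cut. The time is only an example and is worded as a minimum, so a site that applies the rule reaches 120 minutes and satisfies both statements. That is true, but a minimum tells staff what is acceptable, and this one accepts rates the rule forbids.

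Second, the surrounding safeguards are substantial. The infusion is stopped at once, the subject is monitored until the reaction has resolved completely, and a restart happens only if appropriate, under direct physician supervision with resuscitation equipment at hand. Protocol 5.4.3 also allows a 50% dose reduction for a related event after consulting the Medical Monitor. After Grade 3 there is no same-day restart, re-dosing is discussed with the Medical Monitor, premedication is mandatory, and a further reaction ends treatment. These points stand and lower the expected harm, especially for Grade 3, where drug delivery falls by more than half.

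Third, few subjects are likely to be affected. Protocol 1.2.2 reports 9 infusion-site reactions in 6 subjects over 994 infusions in the completed study, 7 of them Grade 1, which leaves at most 2 of higher grade. It also mentions a vasovagal syncope in the parent study. Subjects with a history of Grade 3 or higher infusion-related events are excluded. Former placebo subjects, however, receive the drug for the first time here, so that history cannot screen them.

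Fourth, the dose slip is small below the cap, and the larger gaps for heavy subjects require a site to follow the mg/kg figure over the stated 50%. That also stands.

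Finally, SAP 10 records that the program was discontinued, so new dosing text may change no infusion, and subject-level listings of exposure and dose modifications are already planned.

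**Conclusion.** The contradiction is real. At the stated floor the volume rate falls by 33.3%, not 50%, which is 1.33 times the rate the rule permits. The Grade 3 dose figure is 4.2% above half. The comparison assumes a previous 60-minute infusion and an unchanged 250 mL bag, both as the protocol states.

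The practical weight lies in the Grade 2 restart. For Grade 3 the shortfall is in mL/min only, since drug delivery falls about 65%. The dose error is minor below 104.2 kg; above that it depends on weight and on which instruction a site follows. Affected subjects are probably few, and no planned analysis changes. It should still be corrected, because it is a safety instruction that contradicts itself.

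**What to change.** Keep the 50% rule. In 5.4.2, change the minimum from 90 to 120 minutes in both the Grade 2 and Grade 3 paragraphs, and change the Grade 3 dose to 12 mg/kg (maximum 1250 mg). If the clinical team does intend 90 minutes, restate the rate rule as a one-third reduction. The cost is two time figures, one dose figure and a clarification to sites and pharmacies.

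If dosing has already ended, report in the CSR the doses and infusion rates actually given after Grade 2 and Grade 3 infusion reactions, so that readers do not assume a 50% cut. This adds little work. Protocol 5.5 already captures infusion details and the reasons for adjustments, and Protocol 8.2 and SAP 9.1 already provide subject-level listings. Only the restriction to infusions after a reaction is new.

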5.4.3 Dose Reductions

Dose reductions may be allowed in the event that an observed AE is believed to be related to study drug, and upon consultation between the Investigator and the Medical Monitor, is considered to be manageable by a 50% reduction in dose. The duration of the dose reduction will be at the Investigator's discretion.

5.5 Treatment Compliance

Treatment compliance will be documented in the electronic case report form (eCRF) by recording the date, time, and whether or not each IV dose of study drug was completely infused, along with reasons why treatment was adjusted or not administered, if applicable.

5.6 Prior and Concomitant Medication/Therapy

Prior and concomitant medications include any drug (investigational, prescription, or over-the-counter) or biological product (such as vaccines, blood or blood components) including herbal remedies or preparations. All prior/concomitant medications taken or received by a subject within the 28 days prior to the Month 1-Day 1 Visit through the EOS/ETD Visit, and any changes to concomitant medications during the study, will be recorded in the appropriate eCRF.

5.6.1 Allowed Concomitant Medication/Therapy

- Radiation therapy for the treatment of local amyloid deposits
- Concomitant chemotherapy:
 - The Investigator may prescribe chemotherapy as per standard of care
 - Monthly doses of NEOD001 should not be delayed or skipped due to adjustments made to chemotherapy dosing
 - If bortezomib is administered, antiviral prophylaxis is required

- Particular care must be taken to accurately report chemotherapy administration, including missed or delayed doses, and dose reductions
 - Blood samples for local laboratory assessments must be collected per institutional practice prior to administration of chemotherapy
 - Within 3 days before the first day of a new regimen of chemotherapy, conduct an unscheduled laboratory collection (including hematology, chemistry, prothrombin time/international normalized ratio [PT/INR], and partial thromboplastin time [PTT])
 - If chemotherapy is administered on the same day as NEOD001, the chemotherapy must be administered after the NEOD001 observation period and postdose vital sign measurements
 - Medications such as anti-emetics required for prophylaxis of emesis for the subsequent chemotherapy should be given after the ECG has been completed.
- Calcium channel blockers (if on stable dose)
 - Steroids

5.6.2 Prohibited Concomitant Medication/Therapy

- Other investigational agents (e.g., drugs not approved for any indication)
- Myeloablative chemotherapy with ASCT
- Organ transplant
- Histone deacetylase (HDAC) inhibitors
- Experimental imaging agent directed at amyloid
- Gadolinium contrast agents are only permitted in exceptional circumstances. If a patient requires the use of gadolinium contrast agents, contact the Medical Monitor

6 STUDY PROCEDURES

6.1 Evaluations by Visit

6.1.1 Screening Period: Days -28 to -1

With the exception of the assessments to be considered standard of care (e.g., NT-proBNP), a signed ICF must be obtained before any study-specific screening evaluations are performed and should be documented in the subject's medical chart.

Screening evaluations and procedures will be performed within 28 days prior to the first study drug administration on Month 1-Day 1. Individual test results that do not meet eligibility requirements may be repeated; full rescreening is allowed once per subject.

6.1.1.1 Assessments for Subjects Whose Previous Visit in Study NEOD001-201 was Within 60 Days of Screening

The following will be performed within the 28 days prior to the Month 1-Day 1 Visit:

- Signed ICF
- Review inclusion and exclusion criteria to assess eligibility
- Medical History - Obtain medical history since the subject's last visit in Study NEOD001-201 (including all major hospitalizations and surgeries), as well as the subject's current medical status and therapy for AL amyloidosis
- Prior and concomitant medications/therapy taken or received by a subject within the 28 days prior to the Month 1-Day 1 Visit
- Assessment of AEs
- Complete physical examination - including height (per Section 6.5.1.3)
- Vital signs (HR, BP, RR, and body temperature; per Section 6.5.1.2) - collect after the subject has been at rest for ≥ 5 minutes
- NIS-LL (Appendix 6 and Section 6.5.2.5)
 - Note: NIS-LL is for all subjects who had peripheral neuropathy in Study NEOD001-201
- VASPI (Appendix 7 and Section 6.5.2.5)
 - Note: VASPI is for subjects with painful peripheral neuropathy in Study NEOD001-201
- SF-36v2 (Appendix 8)
 - Note: Administer SF-36v2 before conducting any other assessments on the same calendar day it is administered

- KCCQ ([Appendix 9](#))
 - Note: Administer KCCQ after the SF-36v2, but before conducting any other assessments on the same calendar day it is administered
- 6MWT (Section [6.5.2.3](#)); also collect HR and BP pre- and post-6MWT administration
 - Notes: Two pretreatment 6MWTs are required before the first administration of study drug, with a minimum of 4 days in between the two tests. The first Screening 6MWT is required to be performed between Days -28 and -5, at least 4 days prior to the second Screening 6MWT, which should be performed within 2 days prior to Month 1-Day 1 (i.e., on Day -2 or Day -1). NT-proBNP should be drawn before conducting 6MWT if being performed on the same calendar day.
- 12-lead ECG performed in triplicate (perform centrally)
- Laboratory Assessments (central laboratory, unless otherwise noted) – Note: Laboratory tests results from Study NEOD001-201 that were performed within 28 days of Month 1-Day 1 may be used for screening in this study:
 - Hematology and chemistry (including amylase and creatine kinase) per [Appendix 10](#)
 - Coagulation - PT/INR, PTT
 - Troponin T
 - NT-proBNP
 - Note: NT-proBNP should be drawn before 6MWT if being performed on the same calendar day
 - Urine pregnancy test for WOCBP
 - Note: Women with tubal ligations are considered to be of childbearing potential but women who are surgically sterile (hysterectomy) or postmenopausal ≥ 2 years are not considered to be of childbearing potential
- Other Assessments (see Laboratory Manual):
 - Anti-NEOD001 serum sample

6.1.1.2 Assessments for Subjects Whose Previous Visit in Study NEOD001-201 was ≥ 60 Days from Screening

The following will be performed within the 28 days prior to the Month 1-Day 1 Visit:

- Signed ICF
- Review inclusion and exclusion criteria to assess eligibility

- Medical History - Obtain medical history since the subject's last visit in Study NEOD001-201 (including all major hospitalizations and surgeries), as well as the subject's current medical status and therapy for AL amyloidosis
- Prior and concomitant medications/therapy taken or received by a subject within the 28 days prior to the Month 1-Day 1 Visit
- Assessment of AEs
- Complete physical examination - including height (per Section 6.5.1.3)
- Vital signs (HR, BP, RR, and body temperature; per Section 6.5.1.2) - collect after the subject has been at rest for ≥ 5 minutes
- Eastern Cooperative Oncology Group performance status (ECOG PS) ([Appendix 4](#))
- NYHA class ([Appendix 5](#))
- NIS-LL ([Appendix 6](#))
 - Note: NIS-LL is for all subjects who had peripheral neuropathy in Study NEOD001-201
- VASPI ([Appendix 7](#))
 - Note: VASPI is for subjects who had painful peripheral neuropathy in Study NEOD001-201
- SF-36v2 ([Appendix 8](#))
 - Note: Administer SF-36v2 before conducting any other assessments on the same calendar day it is administered
- KCCQ ([Appendix 9](#))
 - Note: Administer KCCQ after the SF-36v2, but before conducting any other assessments on the same calendar day it is administered
- 6MWT (Section 6.5.2.3); also collect HR and BP pre- and post-6MWT administration
 - Notes: Two pretreatment 6MWTs are required before the first administration of study drug, with a minimum of 4 days between the two tests. The first Screening 6MWT is required to be performed between Days -28 and -5, at least 4 days prior to the second Screening 6MWT, which should be performed within 2 days prior to Month 1-Day 1 (i.e., on Day -2 or Day -1). NT-proBNP should be drawn before conducting 6MWT if being performed on the same calendar day.
- 12-lead ECG performed in triplicate (perform centrally)

- Laboratory Assessments (central laboratory, unless otherwise noted):
 - Hematology and chemistry (including amylase and creatine kinase) per [Appendix 10](#)
 - Coagulation - PT/INR, PTT
 - Troponin T
 - NT-proBNP
 - Note: NT-proBNP should be drawn before 6MWT if being performed on the same calendar day
 - Urine pregnancy test for WOCBP
 - Note: Women with tubal ligations are considered to be of childbearing potential but women who are surgically sterile (hysterectomy) or postmenopausal ≥ 2 years are not considered to be of childbearing potential
 - sFLCs
 - Serum immunofixation electrophoresis (IFE) and protein electrophoresis (PEP)
 - Urinalysis - dipstick per [Appendix 10](#)
 - 24-hour urine collection for:
 - Urine IFE and PEP
 - Urine protein excretion
- Other Assessments (see Laboratory Manual):
 - Anti-NEOD001 serum sample

